#### **8.1.3.2 Solicited Adverse Events**

Within this CTP solicited AEs are defined as all symptoms specifically listed in the memory aid provided to the subjects following each vaccination. The subjects are requested to monitor and record local symptoms (i.e. pain, redness (erythema), swelling, induration, itching (pruritus) and

vaccination site appearance (normal/healed, red spot, bump, reddish blister, whitish blister, scab, ulcer/crater, warmth, swollen >3in, red streaks, drainage) as well as general symptoms (i.e. body temperature, headache, muscle pain (myalgia), chills, nausea, fatigue, malaise, swollen lymphnodes) in the memory aid daily for the day of vaccination and the following 14 days (days 0-14, 15 day period). Any symptoms persisting beyond Day 14 post vaccination are recorded in a memory aid extension. The definition of AEs originates from the MVA-BN® Investigator's Brochure and the ACAM2000® Prescribing Information ([Appendix IVc](#); [Section 17.7](#)).

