3.7.1 Full Analysis Set

The Full Analysis Set (FAS) consists of all subjects

- i) who had received at least one dose of trial vaccine and
- ii) for whom any post vaccination safety or immunogenicity data are available

The safety analysis and secondary supportive immunogenicity analyses will be performed on the FAS. Subjects in Group 1 who do not receive an MVA-BN[®] vaccination will not be considered enrolled in the trial (although they should receive an ACAM2000[®] vaccination outside of the protocol later).

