3.8 Definitions, Data Conventions and Handling of Missing Data

3.8.1 Missing Data

Analysis of immunogenicity variables will be done on a valid case basis, i.e. for missing observations no imputation technique such as “Last observation carried forward” (LOCF) will be applied, since this could introduce an optimistic bias into the analysis.

For the analysis of safety data incomplete AE and medication start and end dates will be imputed in order to assign these events to the correct vaccination period (see [Section 3.8.2](#)).

Missing Vital Signs data for Visit 1 will be imputed using screening (or latest re-screening) values. However, this will be displayed as ‘Baseline’ values in the tables and listing for Vital Signs data without reference to whether the data originated from Visit 1 or SCR.

All data will be listed and summarized as captured in the eCRF. However, it may be necessary to impute incomplete AE and medication start and end dates in order to assign these events to the correct vaccination period, which will be done as follows:

For prior and concomitant medication and AEs imputation of partial start and end dates will be done for analysis purpose according to the following rules:

Missing	Rule for start date	Rule for end date	Flag for imputation
Day	First of month*	Last of month*	D
Month [†]	1. January*	31. December*	M
Year [†]	no imputation	Last visit date	Y

* Unless the imputed start date is before first visit date, in which case first visit date is used; or the imputed stop date is after last visit date in which case last visit date available is used.

† It is assumed that a missing month implies a missing day as well, and that a missing year implies a missing month and day.

All listings will display the original dates as captured in the eCRF.

For analysis of efficacy data if one or both of the Day 6-8 or Day 13-15 photographs are missing then the photograph will be recorded as missing and the assessment of attenuation will not be made.

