3.9.2 Safety Variables

Physical examination (complete examinations at Visit SCR and targeted physical examination at other visits).

Only abnormal physical examination results will be listed.

Vital signs (at each visit)

- Heart rate [beats per minute]
- Systolic and diastolic blood pressure [mmHg]
- Body temperature [°F]
- Respiratory rate (breaths/min)

12-lead electrocardiogram (ECG) (at SCR and Visit 3 and in Group 1 only Visit 9)

(Additional ECGs will be performed and reported if clinically indicated [e.g. in Group 1 at Visit 6], or in case of any clinically significant cardiac events are present)

- Investigator's overall interpretation (normal, abnormal)
- Clinical significance

Safety laboratory data (at SCR, Visit 3 and in Group 1 only Visit 6 and Visit 9)

Clinical chemistry (serum)

- Total bilirubin
- Alkaline phosphatase
- SGOT/AST (Aspartate Aminotransferase)
- SGPT/ALT (Alanine Aminotransferase)
- Serum creatinine
- Sodium
- Potassium
- Calcium
- Troponin I (at SCR and Visit 3 and in Group 1 only Visit 9)

And the following only at SCR

- LDL
- HDL
- Hepatitis B/C –Testing
- HIV Testing
- Total cholesterol

Hematology (whole blood)

- Red blood cell count
- Hemoglobin
- Total and differential WBC (Eosinophils, Basophils, Neutrophils - % and absolute -, Leucocytes, Lymphocytes, Monocytes)
- Platelet count

Pregnancy test (serum β -HCG pregnancy test at SCR or urine β -HCG pregnancy test within 24 hours prior to each vaccination and at last active trial visit for women of childbearing potential.

Results of all pregnancy tests will be listed.

Solicited local AEs reported in the subject memory aid (on days of vaccination and during the following 14 days)

- Injection Site Erythema (Redness)
- Injection Site Swelling
- Injection Site Pain
- Injection Site Induration
- Injection Site Itching (Pruritus)

And vaccination site appearance (normal/healed, red spot, bump, reddish blister, whitish blister, scab, ulcer/crater, warmth, swollen >3inch, red streaks, drainage)

Solicited general AEs reported in the subject memory aid (on days of vaccination and during the following 14 days)

- Body Temperature (Fever)
- Headache
- Myalgia (Muscle pain)
- Chills
- Nausea
- Fatigue
- Malaise
- Swollen Lymph nodes (Lymphadenopathy)

Unsolicited AEs reported (on days of vaccination and during the following 28 days)

- Other, unsolicited local and general adverse events following vaccination

SAEs

AESI

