3.10.6 Compliance

Compliance will be evaluated with respect to the number of vaccine doses received and the number of memory aids completed.

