In addition, the incidence will be calculated by severity (i.e. the number of subjects developing a particular local solicited AE during the 15-day period after each vaccination divided by the number of subjects at the time of the vaccination) with corresponding 95% Clopper-Pearson CI. The incidence will also be calculated for any solicited local AE for each vaccination period and per subject.

The duration of the AEs will be included in the listing. The duration of the AEs will also be summarized using the mean, SD, median, minimum and maximum.

Solicited General AEs

Solicited general AEs will be summarized in the same manner as solicited local AEs.

In addition a similar summary table will be produced for relationship of the AEs to trial vaccine. Also the incidences of causally related AEs, and those with casually related with Grade ≥ 3 will be summarized per vaccination period and overall by subject.

Unsolicited AEs

Treatment emergent unsolicited AEs will be summarized by SOC and PT and vaccination period and by subject.

A summary of the number of AEs by intensity and by relationship to trial vaccination will also be presented.

The number of AEs with a reasonable possibility of being related to the vaccine will be presented in a separate listing and summarized in a table by SOC and PT and vaccination and by subject.

Non-treatment emergent AEs will only be flagged and included in the listing, but will not be included in the tables.

Assessment of ACAM2000[®] Vaccination Site

The following additional four measurements will be derived from the subject's memory aids:

- maximum lesion diameter measured in mm
- maximum erythema measured in mm
- maximum induration measured in mm
- healing time (calculated using date scab fell off)

For descriptive purposes the median for each group (and overall for both groups) will be calculated along with non-parametric confidence intervals for the median (Hahn, 1991). This will be obtained using the SAS Univariate procedure with the option CIPCTLDF. In addition the minimum and maximum value will be displayed.

The medians in Group 1 and Group 2 will be presented along with the 95% non-parametric PB confidence interval of the ratio.

The investigators measurement of the lesion size, erythema and induration will be presented in a similar way for the Day 7, Day 14 and Day 28 post ACAM2000[®] vaccination.

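### SAP 3.10.9 counts vaccinated subjects without memory-aid data in the solicited-AE denominator, so the incidence is generally biased low unless every memory aid is returned

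*SAP*

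**What the plan says.** SAP 3.10.9 takes the subjects with a given solicited local AE "during the 15-day period after each vaccination divided by the number of subjects at the time of the vaccination" and attaches a 95% Clopper-Pearson interval. It adds: "Solicited general AEs will be summarized in the same manner as solicited local AEs".

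The numerator comes from one source. Protocol 8.1.3.2 states that "solicited AEs are defined as all symptoms specifically listed in the memory aid provided to the subjects following each vaccination", and SAP 3.9.2 names the variables in the same terms: "Solicited local AEs reported in the subject memory aid".

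Nothing links the denominator to that source:

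- SAP 3.7.1 admits to the full analysis set any vaccinated subject "for whom any post vaccination safety or immunogenicity data are available". A single blood result is enough.
- SAP 3.8.1 has a rule for immunogenicity: "Analysis of immunogenicity variables will be done on a valid case basis". For safety it deals with dates only: "For the analysis of safety data incomplete AE and medication start and end dates will be imputed". A missing memory aid is not mentioned.
- SAP 3.10.6 evaluates compliance by "the number of vaccine doses received and the number of memory aids completed", and listing 16.2.1.5.3 in SAP 5.2 accounts for memory aids subject by subject. Neither feeds into the incidence.

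**The concern.** A subject who was vaccinated but lost the memory aid, or left before handing it in, adds one to the denominator and usually cannot add to the numerator. In effect that subject is scored as having had no reaction. The rate then estimates the chance of reacting multiplied by the chance of having memory-aid data, whereas the endpoint is the occurrence of solicited reactions on days 0 to 14. For a safety endpoint, a downward error is not the cautious direction.

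Comparing the reactogenicity of ACAM2000 alone with ACAM2000 after MVA-BN is a stated secondary objective (SAP 1.2.2), and SAP 3.10.1 plans that comparison of the two groups. If return differs between groups, part of any observed difference in reaction rates will be a difference in return.

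SAP 3.10.9 also derives maximum lesion diameter, erythema and induration from the memory aid and summarises them by medians. Those can use only subjects with data, so one source would be analysed on two bases within one section.

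**Working it through.** The documents state no solicited-AE rate and no memory-aid return rate, so there is no planned figure to reproduce. The check is the effect of the denominator.

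**Inputs**

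- N = 220 vaccinated per group (SAP 3.6.1).
- p = 582/873 = 66.7%, injection-site pain after ACAM2000 in vaccinia-naive subjects (Table 3 of the prescribing information, Protocol Appendix IVc). It is an illustration, not a forecast.
- m = share of vaccinated subjects with no memory-aid data. Not given; assumed range 5% to 20%. The 20% in SAP 3.6.1 is a rate of exclusion from the per protocol set, not of memory-aid loss.
- Non-return is assumed unrelated to reactions, except in the bounds below.

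**Single rate**

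Rate under the SAP = p(1 - m). The absolute shortfall is p × m and the relative shortfall is m, whatever the reaction. In whole subjects, with 95% Clopper-Pearson intervals:

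| m | With data | Events | SAP rate (/220) | Rate among those with data |
|---|---|---|---|---|
| 5% | 209 | 139 | 63.2% (56.4 to 69.6) | 66.5% (59.7 to 72.9) |
| 10% | 198 | 132 | 60.0% (53.2 to 66.5) | 66.7% (59.6 to 73.2) |
| 20% | 176 | 117 | 53.2% (46.4 to 59.9) | 66.5% (59.0 to 73.4) |

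**Bounds when non-return may depend on reactions**

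If the rate among returners is 66.7% and m = 10%, the rate among all vaccinated lies between 66.7 × 0.90 = 60.0% (no non-returner reacted) and 60.0 + 10.0 = 70.0% (all reacted). The SAP rule always reports the lower end.

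**Difference between groups after ACAM2000**

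Let a and b be the true rates in Groups 2 and 1, and m2 and m1 their non-return.

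- Reported difference, Group 2 minus Group 1 = a(1 - m2) - b(1 - m1) = (a - b) + (b × m1 - a × m2).
- Bias = b × m1 - a × m2. With a above b, the difference is overstated only if m1/m2 exceeds a/b.
- Equal true rates of 66.7%, m1 = 10%, m2 = 5%: bias = 6.7 - 3.3 = 3.3 points from unrounded values, where the true difference is zero.
- Unequal true rates, using label pain rates of 66.7% (naive) and 505/1371 = 36.8% (previously vaccinated): a/b = 1.81. With m1 = m2 = 10%, bias = 3.7 - 6.7 = -3.0 points, so a true difference of 29.9 is reported as 26.9. With m1 = 20% and m2 = 5%, bias = 7.4 - 3.3 = +4.0 points from unrounded values.

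**Who counts as present**

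Under Protocol 4.2.5, Group 1 subjects withdrawn after the second MVA-BN dose still attend Visit 7 without being vaccinated. The SAP wording could be read to include them. If 2, 5 or 10 of 220 were counted, a 66.7% rate would fall by 0.6, 1.5 or 3.0 points.

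**The case against.** The strongest reply is that an all-vaccinated denominator is a common safety convention and matches the general AE incidence rule in the same section. The secondary comparisons are descriptive (Protocol 9.6), and no test is specified for individual solicited symptoms. The memory-aid listing would let a careful reader see non-return. This limits the consequence, but a per-subject listing does not correct a rate in a table, and the table list in SAP 5.1 includes no summary of memory aids completed.

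A second reply is that a missing memory aid need not mean missing data. The aid is reviewed at the day 6-8 visit as well as collected at day 13-15. Staff transfer the information to the CRF, examine the site and ask about AEs at visits. This stands in part: the bias is smaller if symptoms reported only at a visit count as solicited. The SAP does not say whether they do, so scoring such a subject as reaction-free is the result of applying a silent rule literally and is not stated policy.

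A third reply is that the remedy is imperfect. Requiring one day of data still treats unrecorded days as free of reactions, and the label puts maximum lesion size at days 8 to 10. Dropping non-returners can bias rates upward if people with few reactions return less often. Both points stand, which is why the all-vaccinated rate should be kept alongside.

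A reader might go further and infer that the bias is greatest after Group 1's third vaccination, or that it favours MVA-BN. The documents support neither. They give no return rate by dose or group, and the denominator is reset at each vaccination. At equal non-return, the absolute loss is larger where reactions are more frequent. Percentages computed with loss in Group 1 alone would assume the answer. They would also borrow label rates from previously vaccinated subjects aged 31 to 84, vaccinated more than 10 years before, who are a poor proxy for subjects aged 18 to 42 primed four weeks earlier.

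**Conclusion.** The point holds as a defect in the stated denominator. Whenever a vaccinated subject has no memory-aid data and no visit report is counted instead, the solicited rate falls. If non-return is unrelated to reactions, each rate is scaled by (1 - m) and its interval moves down roughly in proportion: at a true 66.7%, to about 63%, 60% and 53% for m of 5%, 10% and 20%. The actual size is unknown because m is unknown, and it is zero with full return.

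The comparison between groups is distorted by b × m1 - a × m2. Equal loss shrinks a real difference; only sufficiently unequal loss enlarges one. The plan gives no basis for saying which will occur.

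Neither co-primary analysis is touched. The change should still be made before database lock, because it affects a stated secondary objective and is cheap.

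**What to change.** In SAP 3.10.9, for solicited local and general AEs, define the denominator for each vaccination period as subjects in the full analysis set who received that vaccination and have at least one day of memory-aid data for that period. Naming receipt of the vaccination also settles the Visit 7 ambiguity.

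Show by group and period the number vaccinated, the number with memory-aid data and the number without. Keep the all-vaccinated rate as a sensitivity analysis. Leave the unsolicited AE and SAE denominators as they are.

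The cost is a short SAP insertion, a new denominator in tables 15.3.1.2.x and 15.3.1.3.x, and the sensitivity output; the memory-aid accounting data are already to be listed. In return, denominators will vary by period and rates will be slightly higher. Partial diaries will still count as no reaction on unrecorded days, and the new rate will rest on non-return being unrelated to reactions. The last two limits should be stated with the tables.

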3.10.10 Clinical Laboratory Variables (Hematology, Chemistry)

All measured hematology and chemistry values (and changes from baseline for continuous parameters) will be listed and summarized at each visit using descriptive statistics.

Summary tables will be produced for the number of high and low laboratory values at each visit by hematology and chemistry parameters.

In addition, all clinical laboratory values outside the normal range will be listed with screening number, demographic information and flagging of abnormal values (L = Below normal range, H = Above normal range) with their clinical significance.

'Shift tables' will be used to evaluate categorical changes from SCR to Visit 3, SCR to Visit 6 (Group 1 only) and SCR to Visit 9 (Group 1 only) with respect to normal ranges (below, within, above normal range) in hematology and chemistry parameters.

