### Troponin I

Troponin I will be measured at the Screening Visit and at Visit 3, and at Visit 9 for Group 1 only. At any other visits troponin I will only be measured if clinically indicated.

Cardiac events fulfill the definition of an AESI as described in [Section 8.3.2](#). The investigator will be asked to assess the clinical significance of the case.

Case definitions as published by the CDC ([MMWR, May 30, 2003](#)) are provided in [Appendix III; Section 17.3](#) in order to:

- help investigators to recognize possible events of acute myocarditis and/or pericarditis and
- distinguish from unspecific and isolated ECG abnormalities without or with unclear clinical significance.

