first vaccination is defined as Day -1, and so on. In particular, no reference is made to the time of the vaccination in the calculation of the trial day, i.e. at midnight a new trial day begins regardless of the time of first vaccination. Note that it is possible for some Visit 1 procedures to be performed, for example, on trial Day -1 prior to vaccination at Day 0.

Baseline:

If not otherwise specified, 'Baseline' refers to the last measurement before first vaccination of trial drug. This is either at Visit 1 or Screening (SCR), or latest re-screening as appropriate. If there is missing vital sign data at Visit 1 then the Screening Visit or latest re-screening data will be used to impute the missing data. These data will be summarized as Baseline data without direct specification of which visit was used. However, at all other visits no imputation will be used and the actual visit used will be specified in tables or listings.

Screening Phase:

The screening phase is defined from the Screening Visit up to Visit 1 before the first vaccination. This includes any re-screening visits that are conducted.

Active Trial Phase:

All data collected from the first vaccination at Visit 1 up to (and including) either Visit 10 for Group 1 or Visit 4 for Group 2, or trial early termination visit. This could include any unscheduled visits up until Visit 10 or Visit 4, as appropriate.

FU Trial Phase:

The follow-up period begins immediately after the active trial phase and continues until the (remote) FU (Follow-up) Visit.

All data collected after Visit 10 for Group 1 and Visit 4 for Group 2 until, and including, the remote FU Visit (and if performed on-site FU Visit). Note that for some subjects for whom the remote FU Visit was not performed there may not be any FU phase data available, however this will not be considered a protocol deviation.

Eligible Subjects:

A subject is eligible if the question "is the subject eligible for the trial?" is answered with "yes" and there are no subsequent major protocol deviations that affect the eligibility of the subject.

Subjects Receiving Vaccinations:

A subject received trial vaccination according to the randomized group assignment if a date of drug administration is given for the vaccination and no major vaccine handling deviation is recorded on the electronic Case Report Form (eCRF).

Treatment Emergent Adverse Event:

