3.10 Analysis and Presentation Methods

3.10.1 Listings and Descriptive Statistics

All individual data entered in the eCRF and derived data will be listed as measured in the Individual Subject Data Listing.

For ELISA and PRNT titers descriptive statistics will be based on Geometric Means and confidence intervals (CI). For other, continuous parameters, measurements will be summarized by means of descriptive statistics (i.e. number of observations (N), mean, SD, minimum (Min), median, maximum (Max)) and categorical data will be summarized by means of frequency tables (i.e. count and percentages) and CI, if not stated otherwise.

All tables and listings will be sorted by scheduled visit (and subject, if appropriate).

All tables will be presented split by treatment groups (Groups 1 and 2). A comparison of the ACAM2000[®] vaccination phase will also be presented between Groups 1 and 2.

Repeat assessments/measurements and unscheduled assessments/measurements will be included in the Individual Subject Data Listing. All other repeat values will be listed in a separate listing.

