3.10.11 Vital Signs and ECG

Measured vital signs values and changes from Baseline will be summarized at each time point using descriptive statistics. All measured values will be listed.

The investigator's overall interpretation of either normal, abnormal and if abnormal whether the ECG is clinically significant or not clinically significant, will be summarized at Screening and Visit 3. All ECGs including those clinically indicated and those not clinically indicated will be listed. In addition shift tables between SCR and Visit 3 and between SCR and Visit 9 (Group 1 only) will be produced to summarize the number of changes in ECG status.

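### Group 1 laboratory, troponin, ECG and vital-sign changes after ACAM2000 are measured from before the first MVA-BN dose, so the planned tables cannot separate sub-clinical MVA-BN-phase changes from later ones

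*SAP*

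**What the plan says.** The SAP's General Definitions give one Baseline, which "refers to the last measurement before first vaccination of trial drug". No second baseline is defined for the ACAM2000 phase of Group 1.

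- **Laboratory (SAP 3.10.10).** Shift tables are to "evaluate categorical changes from SCR to Visit 3, SCR to Visit 6 (Group 1 only) and SCR to Visit 9 (Group 1 only"). Continuous parameters are also summarized as change from baseline. Troponin I is listed under clinical chemistry in SAP 3.9.2, so it follows the same rule.
- **ECG (SAP 3.10.11).** "shift tables between SCR and Visit 3 and between SCR and Visit 9 (Group 1 only) will be produced".
- **Vital signs (SAP 3.10.11).** "Measured vital signs values and changes from Baseline will be summarized at each time point using descriptive statistics". Baseline here is Visit 1, with screening used only if Visit 1 is missing.
- **Comparison (SAP 3.10.1).** A comparison of the ACAM2000 "vaccination phase will also be presented between Groups 1 and 2". Comparing the safety of ACAM2000 alone with ACAM2000 after MVA-BN is a secondary objective (Protocol 3.2, SAP 1.2.2).

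Adverse events are treated differently. SAP 3.8.2 assigns each one to a vaccination period, and Period 3 in Group 1 starts at the ACAM2000 dose.

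The sampling schedule limits what can be used as a later reference. "Troponin I will be measured at the Screening Visit and at Visit 3, and at Visit 9 for Group 1 only" (Protocol 8.2.7). The same section makes the Visit 6 ECG conditional on clinical indication. Safety laboratory samples are routine at Visit 6 (Protocol 8.2.8). Vital signs are taken at Visit 7 before ACAM2000 is given (Protocol 4.2.2).

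**The concern.** Visit 9 is the two-week post-ACAM2000 assessment in Group 1, and Visit 3 is its counterpart in Group 2. In Group 2 the screening reference precedes ACAM2000 and nothing else. In Group 1 the same reference precedes two MVA-BN doses as well. A Group 1 shift from screening to Visit 9 therefore mixes change during the MVA-BN phase, change after ACAM2000 and background change over a longer time. Setting it beside the Group 2 shift from screening to Visit 3 compares unlike quantities.

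What is at stake is the reading of sub-clinical shifts. The documents show that such changes are plausible in both phases. Protocol Table 1 lists raised troponin I, raised hepatic enzymes and lowered white cell count as uncommon suspected reactions to MVA-BN. The ACAM2000 prescribing information (section 5.1.3, Appendix IVc) reports that 8 of 10 suspected myocarditis cases, across ACAM2000 and Dryvax recipients, were sub-clinical and found only by ECG, with or without troponin I elevation.

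**Working it through.** The plan states no figure for these intervals, so there is none to reproduce. The check is visit-window arithmetic followed by a test of what the planned tables can show.

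**Inputs** (Protocol 1.5 and 4.2, days from Visit 1):

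- Screening: −70 to −1. Visit 3: 13 to 15. Visit 4: 27 to 29. Visit 7: 55 to 57.
- Visit 6 = Visit 4 + 13–15: 27+13 = 40 to 29+15 = 44.
- Visit 9 = Visit 7 + 13–15: 55+13 = 68 to 57+15 = 72.

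**Formula.** Shortest interval = earliest later visit − latest reference visit. Longest interval = latest later visit − earliest reference visit.

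| Measure | Group | Reference to visit | Interval (days) | MVA-BN doses between |
|---|---|---|---|---|
| Laboratory, troponin I, ECG, as planned | 2 | Screening to V3 | 13+1 = 14 to 15+70 = 85 | 0 |
| Laboratory, troponin I, ECG, as planned | 1 | Screening to V9 | 68+1 = 69 to 72+70 = 142 | 2 |
| Vital signs, as planned | 2 | V1 to V3 | 13 to 15 | 0 |
| Vital signs, as planned | 1 | V1 to V9 | 68 to 72 | 2 |
| Laboratory, later reference | 1 | V6 to V9 | 68−44 = 24 to 72−40 = 32 | 0 |
| Vital signs, later reference | 1 | V7 to V9 | 13 to 15 | 0 |
| ECG, troponin I, later reference | 1 | V3 to V9 | 68−15 = 53 to 72−13 = 59 | 1 (second dose) |

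**Can the planned tables separate the phases?** Take two Group 1 subjects with a normal laboratory value at screening.

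- Case A: the first is abnormal at both Visit 6 and Visit 9; the second stays normal.
- Case B: the first is abnormal at Visit 6 only; the second is abnormal at Visit 9 only.

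Both cases put one normal-to-abnormal shift in the screening-to-Visit 6 table and one in the screening-to-Visit 9 table, so the planned tables are identical. A Visit 6 to Visit 9 table differs: no new abnormality in A, but one new and one resolved in B.

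**Direction.** Normal at screening, abnormal before ACAM2000 and still abnormal at Visit 9 is tabulated as a shift at Visit 9, although nothing changed after ACAM2000. Abnormal at screening, normal before ACAM2000 and abnormal again at Visit 9 is tabulated as no shift, although a change followed ACAM2000. The error can go either way.

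**Size, as an illustration only.** Let p be the rate of shifts arising after ACAM2000 and q the rate of shifts arising earlier and persisting to Visit 9. Treat the two as independent, and ignore the masking case. The apparent rate is 1 − (1−p)(1−q), so the excess among 220 subjects is 220 × q × (1−p). With p = 5% assumed:

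- q = 0: 0 subjects
- q = 1%: 220 × 0.01 × 0.95 = 2.1 subjects
- q = 10%: 220 × 0.10 × 0.95 = 20.9 subjects

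Neither p nor q is in the documents. The nearest figure is the uncommon band in Protocol Table 1 (1/1,000 to below 1/100), which is 0.22 to 2.2 of 220. That band counts suspected drug reactions. It does not count all shifts, and it does not say whether they persist.

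**The case against.** The case for leaving the plan alone has several sound parts.

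- **Screening is a defensible reference.** It has the same meaning in both groups, precedes all trial vaccine and is protected by randomization. A pre-ACAM2000 reference in Group 1 is post-randomization and exists only for those who got that far. This stands, and is why the screening tables should stay and the new ones be additions.
- **The important findings are handled elsewhere.** Clinically significant ECG abnormalities and troponin I at or above 2×ULN are among the criteria for withholding further vaccination in Group 1 (Protocol 4.2.5). They are also AESIs (Protocol 8.1.3.3), with a per-period table (SAP Table 15.3.2.3). Clinically significant or Grade 3–4 laboratory values are recorded as adverse events (Protocol 8.1.3.1) and assigned to a vaccination period (SAP 3.8.2). This stands, and confines the point to sub-clinical changes.
- **The comparison is promised only in general terms.** SAP 3.10.1 does not name these data, SAP 5.1 lists no dedicated ACAM2000-phase table for them, and the tables are labelled by visit. This is fair, but a reader following 3.10.1 has only these references to use.
- **Existing output helps.** There is a screening-to-Visit 6 laboratory table, a Visit 7 vital-sign summary, and listings from which persistence can be traced subject by subject. This is true, but no planned summary shows within-subject change across the ACAM2000 dose.
- **The repair is incomplete for cardiac measures.** A Visit 3 reference still precedes the second MVA-BN dose. This stands and must be stated as a limit.

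**Conclusion.** The point holds for sub-clinical laboratory, troponin I, ECG and vital-sign changes. The ACAM2000-phase comparison would set 69–142 days and two MVA-BN doses in Group 1 against 14–85 days and no other vaccine in Group 2. For vital signs it is 68–72 against 13–15 days. The interval arithmetic rests only on the protocol's visit windows. The effect on the counts is unknown, and is zero if every subject enters the ACAM2000 phase in the same category as at screening.

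A reader might infer more, and the documents do not support it:

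- That the comparison is biased against priming. The masking case runs the other way, so the direction is not fixed.
- That the two vaccines' contributions can never be separated. They can be traced in the listings, but they are not tabulated.
- That serious cardiac signals would be misattributed. The withdrawal criteria and the per-period AESI and adverse-event tables largely cover these.
- That the 142-day maximum applies to every measure. It does not apply to vital signs with a Visit 1 baseline.

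The affected output is descriptive secondary safety reporting. Neither co-primary test changes. The change is worth making because it is cheap and brings the promised comparison closer to like-for-like.

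**What to change.** Keep all screening-based tables. Add the following for Group 1, and list them in SAP 5.1:

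- **Laboratory, excluding troponin I:** Visit 6 to Visit 9 shift and change tables, beside the Group 2 screening-to-Visit 3 tables.
- **Vital signs:** change from the Visit 7 pre-vaccination value to Visits 8, 9 and 10, beside the Group 2 changes from Visit 1. Protocol 1.5 marks vital signs at Visit 10, but the Visit 10 task list in Protocol 4.2.2 omits them; these must be reconciled first.
- **ECG and troponin I:** Visit 3 to Visit 9 shifts, with Visit 3 as the fixed reference. A rule taking the last value before Visit 7 would use Visit 6 ECGs only from subjects with a clinical indication, and so would mix reference times selectively.

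State two limits beside the tables. The Visit 3 to Visit 9 interval still contains the second MVA-BN dose. All the added tables cover only Group 1 subjects who received ACAM2000, so they are not a fully randomized comparison.

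The cost is SAP wording and a few extra tables from data already scheduled for collection. No visit, sample or sample-size change is needed.
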